10.3 Go/No-Go Milestones

A set of criteria are to be defined for the safety and tolerability of each of the dose-escalation cohorts (Cohorts A-C or Steps 1-3), in order to proceed to the next higher dosage cohort.

Any dose of vaccine which results in more than one episode of a grade 2 or higher solicited local or systemic adverse event of the same category, may be considered too reactogenic for dose-escalation, unless the SMC recommends otherwise.

A set of *a priori* safety and immunologic benchmarks for the dose-selection of the vaccines in Part 2 of the study (Cohort D) is defined. The highest well tolerated dosage (no more than one grade 2 or higher solicited symptom of the same category) will be selected for further evaluation in Part 2 of the study. Furthermore, the serum antigen-specific ELISA IgG response rates will also be evaluated for dosage selection. Optimally, the final targeted dosage will result in at least 70% response rates with the target dosage of vaccine.

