1.3.2 GLP Toxicology Study

As part of our submission of an Investigational New Drug Application (IND) to the U.S. Food and Drug Administration (FDA), the four products manufactured at Bharat Biotech International, Inc. and two of which are to be tested in the Phase 1 trial described herein have been evaluated in a Rabbit Toxicology Test performed by Noble Life Sciences, a Contract Research Organization located in Sykesville, [name], that specializes in performing animal toxicology tests under the tenets of Good Laboratory Practices (GLP). Eighty pathogen-free rabbits, 40 males and 40 females, were injected; 20 rabbits with each vaccine test product (3 vaccine test products: single-dose bivalent, multi-dose bivalent, and multi-dose trivalent) and 20 with the placebo test product (buffer containing 2-phenoxyethanol). The Rabbit Toxicology study was initiated July 20, 2018 and the first dose of study vaccines were administered on August 13, 2018; a total of four sequential doses separated by 28 days was administered. All animals survived to the scheduled necropsy. There were no test article-related adverse changes in mortality, clinical observations, physical exams, injection site scores, body weights, food consumption, organ weights, organ-to-body weight ratios, body temperature, ophthalmology or urinalysis. The antigen-specific ELISA IgG responses following the first dose of vaccine for the 20 rabbits that received the trivalent multi-dose test article are shown in the table below. According to these pre-clinical data, the vaccines appear to be immunogenic after a single dose.

ELISA IgG response following the first dose of vaccine for rabbits that received the trivalent multi-dose vaccine				
Typhimurium titers (EU/mL)	Enteritidis titers (EU/mL)		Typhi Vi titers (EU/mL)	
GMT, pre	3.4	GMT, pre	7.2	GMT, pre
GMT, post (day 29)	1454.2	GMT, post (day 29)	4381.4	GMT, post (day 29)
Geometric Mean Fold-rise	426.8	Geometric Mean Fold-rise	610.6	Geometric Mean Fold-rise
Minimum fold-rise	41.0	Minimum fold-rise	75.6	Minimum fold-rise
Maximum fold-rise	6977.1	Maximum fold-rise	3202.8	Maximum fold-rise

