2.3 Primary Objectives and Outcome Measures

The primary objectives and outcome measure of this study are the following:

1. Safety and Reactogenicity: To assess the frequency and severity of solicited local (i.e., injective site) and systemic (such as fever) AEs during the first 7 days following each dose of vaccine.
2. Safety: To assess the frequency and severity of unsolicited AEs within 28 days of each dose of vaccine and the occurrence of any SAEs through 6 months after the last dose of vaccine
3. Immunogenicity: To measure the proportion of subjects that achieve a four-fold increase in titer, as compared to baseline, of specific serum IgG anti-COPS (S. Enteritidis or S. Typhimurium), anti-Vi (S. Typhi) polysaccharide, and anti-FliC (S. Enteritidis or S. Typhimurium) antibody at days 29 and 57, as measured by ELISA.

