8 ASSESSMENT OF IMMUNOGENICITY

8.1 Enzyme-linked Immunosorbent Antibody Assay (ELISA)

The serum IgG levels against the respective antigens will be measured, as previously described.^{15,17,18} Briefly, 96-well plates are coated with the respective COPS, Vi, or FliC antigen (5 µg/mL). After overnight incubation, plates are washed and sera are tested in serial dilutions. Specific antibodies will be detected using peroxidase-labeled anti-human IgG and 3,3,5,5-Tetramethylbenzidine (TMB) substrate. Test and control sera are run in duplicate. Titers are calculated by interpolation of absorbance values of test samples into the linear regression curve of a calibrated control (reference serum). The endpoint titers will be reported as ELISA units (EU), which represent the inverse of the serum dilution that produces an absorbance value of 0.2 above the blank. Seroconversion will be defined as a 4-fold increase in the antibody titer after immunization.

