10 STATISTICAL CONSIDERATIONS

10.1 Study Hypothesis and Sample Size Considerations

The overarching hypothesis of this phase 1 study is that the trivalent *S. Enteritidis/S. Typhimurium/S. Typhi* Vi conjugate vaccine will be well-tolerated at all three dosage levels tested and that the highest dosage level will elicit the strongest serum anti-COPS, anti-FliC and anti-Vi antibody responses in humans. The primary hypothesis of safety will be fulfilled if no participants develop a vaccine related SAE and each vaccine is well-tolerated. The secondary hypothesis of immunogenicity will be fulfilled if each vaccine elicits an immune response by ELISA.

The trial sample size is intended to minimize the number of subjects exposed to each vaccine until sufficient safety data have accumulated to proceed to larger trials. The phase 1 trial sample size was not derived to achieve a pre-specified statistical power. Instead, the sample size was selected to descriptively evaluate the safety and immunogenicity of these vaccines in a first-in-man trial. As a result, there will be sufficient power to detect only very large differences in immunological responses among groups, and confidence limits will be fairly wide.

The endpoint measures for the primary, secondary and exploratory objectives are listed in Sections 6.1, 6.2 and 6.3.

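### Section 10.3 brings only a threshold response rate into Part 2 dosage selection, although the dosage question is about strength of response; a baseline-adjusted log-titer ratio should be named beside it

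*Combined protocol and SAP*

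**What the plan says.** Section 10.1 states the dosage hypothesis: "the highest dosage level will elicit the strongest serum anti-COPS, anti-FliC and anti-Vi antibody responses in humans". The Part 2 text in section 2 likewise aims for the most immunogenic dosage that is well tolerated.

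The primary immunogenicity objective in section 2.3 is "To measure the proportion of subjects that achieve a four-fold increase in titer, as compared to baseline", for two COPS antigens, Vi and two FliC antigens at Days 29 and 57. Section 8.1 uses the same cut: "Seroconversion will be defined as a 4-fold increase in the antibody titer after immunization".

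Section 10.3 sets the Part 2 selection rule, and tolerability comes first: "The highest well tolerated dosage (no more than one grade 2 or higher solicited symptom of the same category) will be selected". It then adds that "the serum antigen-specific ELISA IgG response rates will also be evaluated for dosage selection", with an optimal level of "at least 70% response rates with the target dosage of vaccine". It does not define response. The four-fold rise is the only serum ELISA response definition elsewhere in the protocol.

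Section 10.2 plans a confidence interval for each response proportion. For titers it plans t-based intervals on the log scale for differences between pairs of vaccine groups, reported as GMT ratios. Section 2.4 makes the GMT a secondary objective. Section 2 also has antibody levels measured for the interim analysis before Part 2, but states no rule for using them.

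**The concern.** The ELISA gives a continuous titer and the hypothesis is about its size, yet the selection section takes in only whether each person crossed a fixed cut. Two dosages that both clear the cut in nearly everyone look the same on that measure, even if one produces several times the antibody of the other.

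The only readable fold-rise figures in the protocol lie far above the cut. They come from the GLP toxicology study, for "the 20 rabbits that received the trivalent multi-dose test article". At stake is whether the Part 2 selection review receives usable information on which dosage is most immunogenic.

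**Working it through.** **Protocol's own figure.** The section 1.3.2 table reads "Geometric Mean Fold-rise 426.8 Geometric Mean Fold-rise 610.6", for *S.* Typhimurium and *S.* Enteritidis. Post/pre GMT gives 1454.2/3.4 = 427.7 and 4381.4/7.2 = 608.5. Both agree with the table within the rounding of the pre-dose GMT.

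**Distance from the cut.** The rabbit minima are 41.0 and 75.6, and 41.0/4 = 10 and 75.6/4 = 19. All 20 animals were therefore responders for both antigens.

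**Spread.** For n=20 normal values the expected range is 3.735 SD. From the table's minima and maxima:
- *S.* Typhimurium: ln(6977.1/41.0)/3.735 = 5.137/3.735 = 1.375
- *S.* Enteritidis: ln(3202.8/75.6)/3.735 = 3.746/3.735 = 1.00

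**Group sizes at Day 29, before any second dose (section 2).** 6.25 mcg: 8. 12.5 mcg: 10+4+4 = 18. 25 mcg: 6+6 = 12.

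**Response rate.** With GMFR the geometric mean fold-rise, P(fold-rise ≥ 4) = Φ[(ln GMFR − ln 4)/SD]. At GMFR 426.8 and SD 1.375, Φ[(6.056 − 1.386)/1.375] = Φ(3.40) = 99.97%. At a quarter of that mean (106.7), Φ(2.39) = 99.2%.

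**Power, 25 mcg (n=12) v 6.25 mcg (n=8), two-sided 5%.** The rate uses exact enumeration of Fisher's test. The log scale uses the noncentral t with 18 df and noncentrality ln(ratio)/[SD·√(1/12 + 1/8)], where the square root is 0.456. For a four-fold difference, 1.386/0.456 gives 3.04 at SD 1.0 (power 82%) and 2.21 at SD 1.375 (55%). For a two-fold difference the values are 1.52 (30%) and 1.10 (18%). Log-scale power does not depend on the GMFR.

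| GMFR at 25 mcg | Responders 25 v 6.25 mcg, four-fold difference, SD 1.375 | Power on rate, four-fold difference | Power on rate, two-fold difference |
|---|---|---|---|
| 427 | 99.97% v 99.2% | <0.1% | <0.1% |
| 100 | 99.0% v 90.9% | 0.2-3% | <0.1-0.2% |
| 50 | 96.7% v 79.6% | 7-14% | 0.2-2% |
| 20 | 87.9% v 56.5% | 27-44% | 8% |
| 10 | 74.7% v 36.6% | 27-50% | 8-13% |
| *Log scale, any GMFR* | | *55-82%* | *18-30%* |

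Ranges cover SD 1.0 to 1.375. At equal SD, the rate loses at least 28 points for a four-fold difference (55.2 − 27.2) and at least 10 for a two-fold difference (18.2 − 8.1).

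**The 70% benchmark.** A 70% rate corresponds to a GMFR of 4·exp(0.524·SD), or 6.8 to 8.2. If 25 mcg has GMFR 100 and 6.25 mcg has 25, the lower dosage meets 70% (at least 6 of 8) with probability 97% or more. At GMFR 10 in the lower group this falls to 67-84%, and at GMFR 5 to 25-29%.

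**Adjacent dosages.** For 12.5 mcg (n=18) v 25 mcg (n=12) with a two-fold difference, log-scale power is only 26-44%.

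**The case against.** The strongest reply is that the plan already has a log-scale comparison. The pairwise GMT ratios in 10.2 address the dosage hypothesis directly, and no Fisher test between dosages is planned. This largely stands. A reader might infer that the trial cannot answer its dosage hypothesis; the documents do not support that. Fisher's test serves here only as a yardstick for what the rate can show. The table also does not measure the gain of a fold-rise ratio over the planned GMT ratio, because the documents give no correlation between baseline and Day 29 titers. What remains is that the planned ratio is not described as adjusted for Day 1 titer. The 6.25 mcg contrast runs across sequentially enrolled small cohorts; only 12.5 v 25 mcg has a concurrent randomized comparison, within Cohort C. And 10.3 does not use the ratio.

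Second, 10.3 does not rank dosages by response rate. Tolerability decides first and 70% is a soft check, so a lower dosage that also passes need not change the choice. This stands and limits the consequence.

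Third, a reader might take the rabbit data as showing that the cut saturates in people. They do not. The animals started at 3.4 and 7.2 EU/mL, the dose is not stated, and values are readable for two of five antigens. Section 1.3.1 reports lower FliC than COPS responses in rabbits, and section 2.1 says no human data exist for COPS conjugates. The table shows no saturation at a GMFR of about 20 or below.

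Finally, the trial is descriptive, and Part 2 may not be conducted. Both are true. Small samples limit either analysis, but they are no reason to discard magnitude as well.

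**Conclusion.** The point holds as a gap in the selection section. Section 10.3 leaves response undefined and names only a rate, while 10.1 and the Part 2 aim concern strength. For 25 v 6.25 mcg, a true four-fold difference gives <0.1% to 50% power on the rate against 55-82% on the log scale; a two-fold difference gives <0.1% to 13% against 18-30%.

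These figures assume log-normal fold-rises, a common SD taken from the range in 20 rabbits, full group sizes at Day 29, and four-fold as the meaning of response. The low end applies only if human fold-rises are very high, which is unknown. The four-fold proportion remains a reasonable descriptive primary outcome. The change is worth making because it is nearly free.

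**What to change.** In section 10.2, report the Day 29 geometric mean fold-rise from Day 1, per antigen and dosage, with a 95% CI. Make the between-dosage ratio baseline-adjusted, using either log Day 29 titer with log Day 1 titer as covariate or the ratio of fold-rises on the log scale. Name that ratio, with its 95% CI, as the analysis of the 10.1 dosage hypothesis.

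In section 10.3, state that response means the four-fold rise, and that the selection review considers this ratio beside the 70% response rate. Leave the tolerability rule unchanged and keep the four-fold proportion as the descriptive primary outcome.

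The cost is wording in section 10 and one more estimate per antigen in the interim report. The Day 1 and Day 29 ELISA values are already collected, so no visit, sample or participant is added. The intervals will stay wide at these sample sizes, and the text should say so.

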11 ETHICS/PROTECTION OF HUMAN SUBJECTS

11.1 Ethical Standard

The principal investigator will ensure that this trial is conducted in full conformity with the principles of the Belmont Report: Ethical Principles and Guidelines for the Protection of Human Subjects of Research of the National Commission for the Protection of Human Subjects of Biomedical and Behavioral Research (April 18, 1979) and codified in 45 CFR 46, 21 CFR 50 and 56, and ICH E6; 62 Federal Regulations 25691 (1997), if applicable. The principle investigator's institution (University of Maryland, Baltimore, UMB) will hold a current Federal Wide Assurance (FWA) issued by the Office of Human Research Protection (HRPO).

11.2 Institutional Review Board

The local institution must provide for the review and approval of this protocol and the associated informed consent documents by an appropriate ethics review committee or Institutional Review Board (IRB). Any amendments to the protocol or consent materials must also be approved before they are placed into use unless it is in the best interest of the subjects' safety to implement changes prior to approval. In both the United States and in other countries, only institutions holding a current U. S. Federal-Wide Assurance issued by the Office for Human Research Protections (OHRP) may participate.

Refer to: <http://www.hhs.gov/ohrp/assurances/>

Prior to enrollment of subjects into this clinical study, the protocol and the informed consent form(s) will be reviewed and approved by the appropriate IRB. Any amendments to the protocol or consent materials will also be reviewed and approved by the appropriate IRB. The responsible official for the IRB will sign the IRB letter of approval of the protocol prior to the start of this clinical study. Should amendments to the protocol be required, the amendments will be submitted to the IRB; an IRB letter of approval of the amendment must be obtained prior to acting upon the amendment in the protocol.

The contact information for the local IRB and the Human Research Protections Office (HRPO) is:

University of Maryland, Baltimore
Human Research Protections Office
[name]
Baltimore, MD 21201, U.S.A.
[contact]

11.3 Informed Consent Process

Informed consent is a process that is initiated prior to the individual's agreeing to participate in the study and continues throughout the individual's study participation. Extensive discussion of risks and possible benefits of this therapy will be provided to the participant. Consent forms describing in detail the study, study procedures and risks are given to the potential participant and written documentation of informed consent is required prior to starting any study procedure. Consent forms will be IRB-approved and the participant will be asked to read and review the document. Upon reviewing the document, the investigator will explain the research study to the

participant and answer any questions that may arise. The participants will sign the informed consent document prior to any procedures being done specifically for the study. The participant should have the opportunity to discuss the study with their surrogates or think about it prior to agreeing to participate. The participant may withdraw consent at any time throughout the course of the trial. A copy of the informed consent document will be given to the participant for their records. The rights and welfare of the participant will be protected by emphasizing to them that the quality of their medical care will not be adversely affected if they decline to participate in this study

11.4 Exclusion of Women, Minorities, and Children (Special Populations)

This clinical study will include women, children of 18 years of age and older, and all minorities who meet the inclusion/exclusion criteria, regardless of religion, sex, or ethnic background.

11.5 Subject Compensation

Thoughtful consideration has been made toward subject compensation for healthy volunteer participants enrolled into clinical studies involving non-licensed vaccines and experimental infections. The overarching ethical issues which the CVD's compensation scheme attempts to address are: (1) avoidance of "undue inducement", (2) payments which may result in economically disadvantaged populations bearing an overwhelming share of the risks and burdens of research, and (3) payments which may violate the ethical norms of the investigator-subject relationship by turning it into a commercial relationship. The compensation scheme for this study is adopted from the Wage-Payment Model.⁵⁵ Under the Wage-Payment Model, a participant is assumed to require little skill, but does require time, effort, and an expectation of experiencing undesirable or uncomfortable procedures. Therefore, the CVD's compensation rates are calculated to approximate the hourly wages of an unskilled high-risk laborer. The compensation rate used in this study is a standard rate that is used across all of CVD's clinical research. This compensation rate is clearly described in the informed consent form and is unlikely to be unduly coercive.

Subjects at the Pharmaron site will be compensated for their time and participation.

Subject Confidentiality

Subject (participant) confidentiality is strictly held in trust by the investigators, their staff, and the Sponsor. This confidentiality is extended to cover testing of biological samples and other testing in addition to the clinical information relating to participant.

The study protocol, documentation, data, and all other information generated will be held in strict confidence. No information concerning the study or the data will be released to any unauthorized third party without prior written approval of the sponsor.

The study monitor or other authorized representatives of the sponsor may inspect all documents and records required to be maintained by the investigator, including but not limited to, medical records (office, clinic, or hospital) and pharmacy records for the participants in this study. The clinical study site will permit access to such records.

Participant identity data will be contained in paper study records which will be kept in a locked file cabinet and in a secure electronic database, accessible only to authorized users at each clinical site. The study database will be user-restricted and password-protected. The study database will identify participants by a coded study Volunteer ID number assigned by clinical site personnel, thus participants will not be identified by name.

Subject confidentiality and the limits for access to records is described in the informed consent form.

11.6 Future Use of Stored Specimens

It is intended that any remaining specimens at the closure of the study will be stored at the CVD indefinitely and may be used for further immunological analyses. Participants may choose to have their specimens destroyed and must do this in a written request. This is described in the consent form.

12 DATA HANDLING AND RECORD KEEPING

The site principal investigator is responsible for ensuring the accuracy, completeness, legibility, and timeliness of the data reported.

Source data will be generated by the site and collected on data collection forms. Source data will be entered into a REDCap data management system, managed by the Clinical and Translational Research Informatics Center (CTRIC), University of Maryland School of Medicine. REDCap is a secure web-based application for building an electronic database that provides a 21 CFR Part 11, FISMA, and HIPAA-compliant environment. Quality control audits of all key safety, laboratory, and clinical data in the database will be made after data entry has been completed. Coexistent medical conditions, adverse events and other medical events will be coded using MedDRA dictionary. Concomitant medications will be coded using WHO-DD dictionary. When the database has been declared to be complete and accurate, the database will be locked. Any changes to the database after that time will only be by joint written agreement of the study team.

Data reported in REDCap are derived from the data collection forms and should be consistent with the data collection forms or the discrepancies should be explained.

The sponsor and/or its designee will provide guidance to the site principal investigators and other study personnel on making corrections to the data collection forms.

13 PUBLICATION POLICY

All investigators funded by the Wellcome Trust must agree to their Open Access Policy.

<https://wellcome.ac.uk/funding/guidance/open-access-policy>

The Open Access Policy contains the following elements:

1. Expect authors of research papers, monographs and book chapters to maximize the opportunities to make their results available for free
2. Require electronic copies of any research papers that have been accepted for publication in a peer-reviewed journal, and are supported in whole or in part by Wellcome Trust funding, to be made available through PubMed Central (PMC) and Europe PMC as soon as possible and in any event within six months of the journal publisher's official date of final publication (similarly, monographs and book chapters must be made available through PMC Bookshelf and Europe PMC with a maximum embargo of six months)
3. Expect Wellcome-funded researchers to select publishing routes that ensure the work is available immediately on publication in its final published form, wherever such options exist for their publisher of choice and are compliant with our policy
4. Will provide grantholders with additional funding to cover open access charges, where appropriate, in order to meet our requirements
5. Encourage – and where it pays an open access fee, require – authors and publishers to license research papers using the Creative Commons Attribution license (CC-BY) so they may be freely copied and re-used (for example, for text- and data-mining purposes or creating a translation), provided that such uses are fully attributed (CC-BY is also the preferred license for monographs and book chapters)
6. Affirm the principle that it is the intrinsic merit of the work, and not the title of the journal or the publisher with which an author's work is published, that should be considered in making funding decisions.

Therefore, following completion of this clinical trial, the investigators intend to publish the results of this research in a peer-reviewed scientific journal, within 12 months of locking the database. The International Committee of Medical Journal Editors (ICMJE) member journals have adopted a trials-registration policy as a condition for publication. This policy requires that all clinical trials be registered in a public trials registry, such as ClinicalTrials.gov* (<http://clinicaltrials.gov/>), which is sponsored by the National Library of Medicine.

